6.4 PROPHYLACTIC MEDICATIONS, TREATMENTS, AND PROCEDURES

None will be used

6.5 RESCUE MEDICATIONS, TREATMENTS, AND PROCEDURES

If patients develop an infection during the trial, they will be prescribed the appropriate anti-viral or anti-bacterial medication but will continue in the study.

7 ASSESSMENT OF SAFETY

7.1 SPECIFICATION OF SAFETY PARAMETERS

7.1.2 DEFINITION OF SERIOUSADVERSE EVENTS (SAE)

Adverse event means any untoward medical occurrence associated with the use of an intervention in humans, whether or not considered intervention-related (21 CFR 312.32)

Serious adverse event or serious suspected adverse reaction.

An adverse event or suspected adverse reaction is considered "serious" if, in the view of either the investigator or sponsor, it results in any of the following outcomes: death, a life-threatening adverse event, inpatient hospitalization or prolongation of existing hospitalization, a persistent or significant incapacity or substantial disruption of the ability to conduct normal life functions, or a congenital anomaly/birth defect. Important medical events that may not result in death, be life-threatening, or require hospitalization may be considered serious when, based upon appropriate medical judgment, they may jeopardize the patient or subject and may require medical or surgical intervention to prevent one of the outcomes listed in this definition.

7.1.3 DEFINITION OF UNANTICIPATED PROBLEMS (UP)

Unanticipated problems involving risks to participants or others to include, in general, any incident, experience, or outcome that meets all of the following criteria:

- Unexpected in terms of nature, severity, or frequency given (a) the research procedures
 that are described in the protocol-related documents, such as the IRB-approved research
 protocol and informed consent document; and (b) the characteristics of the participant
 population being studied;
- Related or possibly related to participation in the research ("possibly related" means there
 is a reasonable possibility that the incident, experience, or outcome may have been caused
 by the procedures involved in the research); and
- Suggests that the research places participants or others at a greater risk of harm (including physical, psychological, economic, or social harm) than was previously known or recognized. [4]

With these events the following will occur:

- Modification of inclusion or exclusion criteria to mitigate the newly identified risks
- Implementation of additional safety monitoring procedures
- Suspension of enrollment of new participants or halting of study procedures for enrolled participants
- Modification of informed consent documents to include a description of newly recognized risks
- Provision of additional information about newly recognized risks to previously enrolled participants.

7.2 CLASSIFICATION OF AN ADVERSE EVENT

7.2.1 SEVERITY OF EVENT

- **Mild** Events require minimal or no treatment and do not interfere with the participant's daily activities.
- Moderate Events result in a low level of inconvenience or concern with the therapeutic measures. Moderate events may cause some interference with functioning.
- Severe Events interrupt a participant's usual daily activity and may require systemic drug therapy or other treatment. Severe events are usually potentially life-threatening or incapacitating.

7.2.2 RELATIONSHIP TO STUDY AGENT

All AEs will have their relationship to study agent or study participation assessed. Evaluation of relatedness will consider etiologies such as natural history of the underlying disease, concurrent illness, concomitant therapy, study-related procedures, accidents, and other external factors.

The clinician's assessment of an AE's relationship to study agent is part of the documentation process, but it is not a factor in determining what is or is not reported in the study. If there is any doubt as to whether a clinical observation is an AE, the event will be reported. All AEs must have their relationship to study agent assessed. In a clinical trial, the study product will always be suspect. To help assess, the following guidelines are used.

- Related The AE is known to occur with the study agent, there is a reasonable possibility that the study agent caused the AE, or there is a temporal relationship between the study agent and event. Reasonable possibility means that there is evidence to suggest a causal relationship between the study agent and the AE.
- **Not Related** There is not a reasonable possibility that the administration of the study agent caused the event, there is no temporal relationship between the study agent and event onset, or an alternate etiology has been established.

7.2.3 EXPECTEDNESS

The primary investigator will be responsible for determining whether an AE is expected or unexpected. An AE will be considered unexpected if the nature, severity, or frequency of the event is not consistent with the risk information previously described for the study agent.

7.3 TIME PERIOD AND FREQUENCY FOR EVENT ASSESSMENT AND FOLLOW-UP

The occurrence of an AE or SAE may come to the attention of study personnel during study visits and interviews of a study participant presenting for medical care, or upon review of subject questionnaires.

Information to be collected on al AE or SAE includes event description, time of onset, clinician's assessment of severity, relationship to study product, and time of resolution/stabilization of the event. All AEs occurring while on study must be documented appropriately regardless of relationship. All AEs will be followed to adequate resolution.

Any medical condition that is present at the time that the participant is screened will be considered as

baseline and not reported as an AE. However, if the study participant's condition deteriorates at any time during the study, it will be recorded as an AE. UPs will be recorded in the data collection system throughout the study.

Changes in the severity of an AE will be documented to allow an assessment of the duration of the event at each level of severity to be performed. AEs characterized as intermittent require documentation of onset and duration of each episode.

The primary investigator will record all reportable events with start dates occurring any time after informed consent is obtained until 7 (for non-serious AEs) or 14 days (for SAEs) after the last study intervention. At each study visit, the investigator will inquire about the occurrence of AE/SAEs since the last visit. Events will be followed for outcome information until resolution or stabilization.

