3 STUDY DESIGN, OBJECTIVES, AND ENDPOINTS

3.1 DESCRIPTION OF THE STUDY DESIGN

- A Prospective, Randomized, Split-Arm Clinical Study
- Single Center
- Study agent: Sciton's BBL
- Study Interventions: BBL Treatment on Day 0, Day 7, and Day 21
- Evaluations on Day 0, Day 7, Day 14, Day 21, Day 22, Day 51.

This will be a prospective, split-arm clinical study in which 5 subjects will be randomized to which arm will be treated with Sciton's BBL.

All subjects will have their arms shaved prior to the procedure and cleaned thoroughly with alcohol. After the procedure a zinc-based sunscreen will be applied to both arms.

Before each of the four treatments and 30 days after the last treatment, the subjects' number and square area of ecchymoses will be measured by an evaluator. Side effects will be measured on Day 0, 1, 2, 7, 14, 21, 22 and 51. Digital photography of subject's arms will be done on day 0, 7, 14, 21, and 51.

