3.2.3 SECONDARY ENDPOINTS

- 1. Measurement of pain, swelling, blistering, erythema, and all side-effects immediately after each procedure, as well as 24 hours, 48 hours, and 7 days after the procedure.
- 2. Mean absolute difference in the number of skin tears at baseline and 30 days after the last treatment
- 3. The changes in collagen and elastin between untreated and treated skin
- 4. Mean absolute difference in the change in epidermal thickness between treated and untreated skin
- 5. Changes in gene expression between treated and untreated skin

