5.1.2 DURATION OF THERAPY

- The BBL treatment will take approximately 15 minutes
- The last treatment will be done on Day 21

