6.2.5 FINAL STUDY VISIT

Follow-up Visit 2 (Visit 6, Day 51 +/-2 days)

- Record adverse events as reported by participant or observed by investigator.
- Subjects fill out adherence questionnaire and evaluator review to ensure continued eligibility
- Evaluator measures the size and number of bruises and number of skin tears
- Shave bilateral lower arms
- Take digital pictures of subjects' lower arms
- Provide final instructions

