6.2.8 SCHEDULE OF EVENTS TABLE

Procedures	Enrollment/Baseline/1st Treatment Visit 1, Day 0	2 nd Treatment Visit Visit 2, Day 7	3 rd Treatment Visit Visit 3, Day 14	4th Treatment Visit Visit 4, Day 21	Follow Up Visit 1 Visit 5, Day 22	Follow Up Visit 2 Visit 6, Day 51
Informed	Х					
consent Demographics	Х					
Medical history	Х					
Subject Questionnaire Study Intervention Evaluation for adverse effects Digital photos	Х	Х	Х	Х		х
Study Intervention	Х	Х	Х	Х		
Evaluation for adverse effects	Х	Х	Х	Х		Х
Digital photos	Х	Х	Х	Х		Х
Evaluator Measurements	Х	Х	Х	Х		х
Skin Biopsy					Х	

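### The recording window in 7.3 closes before the Day 51 visit, against the plan's other AE rules; and, read per treatment, secondary endpoint 1 has no collection day for 6 of its 16 side-effect readings

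*Combined protocol and SAP*

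**What the plan says.** **Recording window.** Section 7.3 limits the events that the investigator records to those starting after consent and "until 7 (for non-serious AEs) or 14 days (for SAEs) after the last study intervention". It calls them reportable events and does not define the term. Section 5.1.2 (Duration of Therapy) fixes the reference point: "The last treatment will be done on Day 21". Two other sentences in 7.3 have no such limit: "All AEs occurring while on study must be documented appropriately regardless of relationship", and, where a participant's "condition deteriorates at any time during the study, it will be recorded as an AE". Section 7.3 also has the investigator ask about AEs at each visit, covering the time since the previous one. The final visit on Day 51 carries the step "Record adverse events as reported by participant or observed by investigator" (6.2.5), and the row "Evaluation for adverse effects" in the 6.2.8 table is marked for that visit.

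**Side-effect readings.** Secondary endpoint 1 (3.2.3) covers pain, swelling, blistering, erythema and other side effects right after each procedure, "as well as 24 hours, 48 hours, and 7 days after the procedure". Section 3.1 gives the collection days: "Side effects will be measured on Day 0, 1, 2, 7, 14, 21, 22 and 51". The schematic shows home side-effect questionnaires on Days 1 and 2 only. Section 6.1.1 sets the treatment 2 settings from the answers on Days 0, 1 and 2. For treatments 3 and 4 it refers to the post-procedure questionnaire without naming days.

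**The concern.** Safety of the new BBL protocol is the first secondary objective. Under 7.3, a non-serious event starting on, say, Day 35 must be documented by one sentence and falls outside the window of another. Section 2.3.1 lists pigment change, scarring and infection as risks. If staff apply the 7/14-day sentence literally, such an event could go unrecorded when it starts late, even though the Day 51 visit asks about it.

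The second gap affects both description and dosing. Without planned 24 h and 48 h readings after the later treatments, endpoint 1 cannot show how side effects develop as the settings change. The same answers drive those changes: if all are NONE, the next session gains 10 SkinTyte passes and 1 J in Steps 3 and 4.

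**Working it through.** **Inputs.** Four treatments one week apart, on Days 0, 7, 14 and 21 (Précis, schematic, 6.2.8). Final visit on Day 51 ±2 (6.2.5). Recording limits of 7 and 14 days (7.3). Readings at 0, 1, 2 and 7 days after a treatment (3.2.3). Collection days 0, 1, 2, 7, 14, 21, 22 and 51 (3.1).

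**The plan's own figure.** 21 + 30 = 51, which matches the stated study duration of 51 days.

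**Part 1: recording window**

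- Non-serious AEs: 21 + 7 = Day 28. Gap to the final visit: 51 − 28 = 23 days.
- SAEs: 21 + 14 = Day 35. Gap: 51 − 35 = 16 days.
- With the ±2-day windows, treatment 4 falls on Days 19–23 and the final visit on Days 49–53. The AE limit is then Days 26–30, with a gap of 49 − 30 = 19 to 53 − 26 = 27 days. The SAE limit is Days 33–37, with a gap of 49 − 37 = 12 to 53 − 33 = 20 days.
- If the Day 22 biopsy counts as the last intervention, the limits are Days 29 and 36, with gaps of 22 and 15 days.

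On every version the window closes before Day 49, the earliest final visit.

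**Part 2: endpoint 1, read per treatment.** Readings needed: 4 treatments × 4 times = 16 per subject. A reading counts as covered if its day is listed in 3.1.

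| Treatment (day) | Immediate | 24 h | 48 h | 7 days |
|---|---|---|---|---|
| 1 (Day 0) | 0 | 1 | 2 | 7 |
| 2 (Day 7) | 7 | **8** | **9** | 14 |
| 3 (Day 14) | 14 | **15** | **16** | 21 |
| 4 (Day 21) | 21 | 22 | **23** | **28** |

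Bold days are not listed. Missing: 6 of 16 (37.5%), made up of 0 of 4 immediate, 2 of 4 at 24 h, 3 of 4 at 48 h and 1 of 4 at 7 days. With ten treated subjects (Précis) that is 60 of 160; with the five randomized subjects mentioned in 3.1 it is 30 of 80. One bullet in 3.1 lists treatments on Days 0, 7 and 21 only. That would give 4 of 12, but the same section also refers to four treatments.

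**Effect on settings.** Take a subject whose answers are always NONE. SkinTyte passes go 10, 20, 30, 40 over the four treatments. Step 3 goes 10, 11, 12, 13 J and Step 4 goes 8, 9, 10, 11 J. The increase at treatment 2 rests on scheduled Day 1 and Day 2 answers. The increases at treatments 3 and 4 have no scheduled 24 h or 48 h answers behind them.

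**The case against.** **On the window.** The sentence covers reportable events, so one could reconcile the text: document everything, and apply a shorter window to a narrower class. Most other provisions are inclusive. Section 7.2.2 has doubtful observations reported, 7.4.1 sends any AE to the IRB with no end date, and 3.1 lists side effects at Day 51. This largely stands: staff may well record late events anyway. It does not remove the conflict, because the narrower class is never defined and the sentence governs what is recorded.

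A reader might infer that 23 of 51 days (45%) or 16 of 51 days (31%) measures lost safety data. The documents do not support that. They give no timing of events, and an event that starts inside the window but is first reported at Day 51 is not excluded.

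**On the readings.** In endpoint 1, the word each is attached to the immediate reading. If the later times applied to treatment 1 only, the days needed would be 0, 1, 2, 7, 14 and 21, all listed in 3.1, and nothing would be missing. That reading is possible but less natural, since side effects are to be followed over four sessions whose settings change. The count must be stated as conditional on the per-treatment reading.

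A reader might also infer that the Day 22 reading is lost, making 7 of 16, because 6.2.4 and 6.2.8 show no AE step at that visit. That goes too far: 3.1 lists Day 22 and 7.3 requires an AE inquiry at every visit.

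Nor are the later settings chosen blind. AEs are recorded and questionnaires completed at each weekly visit, and blistering after the previous treatment triggers a reduction. The forms are not in the documents, so how far back they ask is unknown. Recall a week later is still not a timed 24 h or 48 h reading.

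**Conclusion.** Both parts hold in limited form.

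1. The 7/14-day sentence in 7.3 conflicts with the rest of the plan's AE rules. It leaves 23 days (non-serious AEs) and 16 days (SAEs) of follow-up under contradictory instructions, or 19–27 and 12–20 days across the visit windows. It is one sentence out of line in a plan that otherwise favours full recording. It does not show that events will be lost.
2. On the per-treatment reading of endpoint 1, 6 of 16 readings per subject have no collection day, even against the fullest list of days, in 3.1. The 48 h reading has a planned day after treatment 1 only. The settings for treatments 3 and 4 rest on answers given right after treatment and on recall at the next weekly visit.

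The second part carries more weight: a timed reading that was never scheduled cannot be recovered later, and it bears on dosing. Neither part touches the primary endpoint.

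**What to change.** - **7.3:** replace the 7/14-day limit with: *All AEs and SAEs with start dates from informed consent to the final (Day 51) visit are recorded; for events located on an arm, the arm is noted.* Systemic events need no arm.
- **3.1 and schematic:** add the existing home side-effect questionnaire at 24 h and 48 h after treatments 2 and 3, and at 48 h and 7 days after treatment 4. Nominally these are Days 8, 9, 15, 16, 23 and 28. Time them from the actual treatment date, because visits may move by 2 days.
- **6.1.1:** state that the 24 h and 48 h answers are used in the settings rules for treatments 3 and 4.
- **6.2.4 and 6.2.8:** show AE evaluation at Day 22, to match 3.1 and the each-visit rule in 7.3.

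**Cost.** A few lines of text, one table mark and six short home forms per subject (10 × 6 = 60 in all), with no extra visits. Some late, possibly unrelated events will be recorded; the relatedness assessment in 7.2.2 already deals with those.

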7.4 REPORTING PROCEDURES

7.4.1 ADVERSE EVENT REPORTING

The IRB will receive notification of any UP, AE, or SAE within 24 hours of discovery by the primary investigator.

All SAEs will be followed until satisfactory resolution or until the site investigator deems the event to be chronic or the adherence to be stable. The primary investigator will be responsible for notifying FDA of any unexpected fatal or life-threatening suspected adverse reaction as soon as possible but in no case later than 7 calendar days after the investigator's initial receipt of the information.

7.4.2 REPORTING OF PREGNANCY

If it is discovered that a subject is pregnant, the subject will discontinue any interventions and continue in the study while continuing safety follow-up until the conclusion of her pregnancy.

7.5 STUDY HALTING RULES

Administration of the study agent will be halted when two SAEs determined to be related are reported. The primary investigator will inform the FDA of the temporary halt and the disposition of the study.

7.6 SAFETY OVERSIGHT & CLINICAL MONITORING

An independent medical expert (medical monitor) will advise the study investigator and monitor participant safety. The role of the Medical Monitor is to 1) Review all AEs on a regular basis throughout the trial; 2) be available to advise the investigators on trial-related medical questions or problems, and 3) evaluate cumulative participant safety data and make recommendations regarding the safe continuation of the study. The Medical Monitor will remain blinded throughout the conduct of the clinical trial unless un-blinding is warranted to optimize management of an adverse event or for other

safety reasons. Clinical site monitoring is conducted to ensure that the rights and well-being of human

subjects are protected, that the reported trial data are accurate, complete, and verifiable, and that the conduct of the trial is in compliance with the currently approved protocol/amendment(s), with GCP, and with applicable regulatory requirement(s).

8 STATISTICAL CONSIDERATIONS

8.1 STATISTICAL HYPOTHESES

Primary Endpoint

$$H_0: \mu_C = 0$$
; $H_1: \mu_C > 0$

- > The null hypothesis is the absolute mean difference in the change from baseline to 30 days after the last treatment on the treatment arm as compared to the non-treatment arm is zero.
- The alternative hypothesis is the absolute mean change from baseline to 30 days after the last treatment on the treatment arm as compared to the non-treatment arm is greater than zero.
 - 1. Let μ_C represent the absolute mean difference between the treated arm as compared to the non-treated arm in the difference in the number of ecchymoses from baseline to 30 days after the last treatment.
 - 2. Let μ_C represent the absolute mean difference between the treated arm as compared to the non-treated arm in the difference in the size of ecchymoses from baseline to 30 days after the last treatment.

A Paired t-test will be used to analyze the primary endpoint. The results of the statistical analysis will be presented as an odds ratio with 95% Confidence intervals. A Shapiro-Wilk Test will be used to assess the normality of data.

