I agree to ensure that all staff members involved in the conduct of this study are informed about their obligations in meeting the above commitments.

Principal Investigator: [name]

_Date: ______ Signature

Title:

A Prospective, Randomized, Split-Arm Clinical Study Investigating the Efficacy and Safety of Sciton's Broad Band for the Treatment and Prevention of Senile Purpura

Précis:

There will be ten subjects, 5 older subjects over 65 years of age with at least one ecchymotic lesion on each arm measuring at least one cm, and 5 subjects under 35 years of age. All subjects will be randomized to undergo 4 Sciton Broad Band Light (BBL) treatments on either their left or right arm one week apart. Subjects will fill out questionnaires, have pictures of their lower arms taken, and will be graded and measured by evaluators regarding the number and size of their ecchymoses as well as side effects such as blistering, pain, erythema, and swelling. One day after their 4th treatment, subjects will have biopsies done to be analyzed for changes in histology and gene expression. The subjects will follow up at 30 days after their last treatments for final pictures of their lower arms and evaluations.

Objectives:

Primary Objectives: To assess the efficacy of BBL in improving the appearance of senile purpura

Important Secondary Objectives:

- 1. To assess the safety of a new BBL protocol for treating and preventing senile purpura
- 2. To assess the efficacy of BBL in reducing skin tears
- 3. To assess the efficacy of BBL to improve the histology of the skin
- 4. To assess the efficacy of BBL to increase epidermal thickness
- 5. To assess the efficacy of BBL to change gene expression

Endpoint

Primary Endpoints:

- Mean absolute difference in the BBL treated arms as compared to the non-treated arms of those with senile purpura in the total square area of purpuric lesions from the first treatment to 30 days after the last treatment
- Mean absolute difference in the BBL treated arms as compared to the non-treated arms of those with senile purpura in the number of purpuric lesions from the first treatment to 30 days after the last treatment

Important Secondary Endpoints:

1. Measurement of pain, swelling, blistering, erythema, and all sideeffects immediately after each procedure, as well as 24 hours, 48 hours, and 7 days after the procedure.

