3.2.2 PRIMARY ENDPOINT

➤ Primary Endpoint: Mean absolute difference between the treated and non-treated arms in the change of total square area and number of ecchymoses from baseline to 30 days after the last treatment.

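### The primary result is to be reported as an odds ratio, although the endpoints, null value and test all concern a mean difference

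*Combined protocol and SAP*

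**What the plan says.** The SAP and protocol section 8.1 carry the same text on the primary analysis. The hypotheses are set on a mean difference. One begins "The null hypothesis is the absolute mean difference in the change from baseline to 30 days after the last treatment" and gives the null value as zero; the alternative is that the quantity "as compared to the non-treatment arm is greater than zero". The parameter is then defined twice, once for the number of ecchymoses and once for their size.

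Three statements on method follow. The first names the test: "A Paired t-test will be used to analyze the primary endpoint". The second, directly after it, sets the form in which the findings are to be reported: "The results of the statistical analysis will be presented as an odds ratio with 95% Confidence intervals". The third adds a check on the distribution: "A Shapiro-Wilk Test will be used to assess the normality of data".

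The endpoints are numeric wherever they are defined. The protocol synopsis lists two primary endpoints, one for total area and one for number of lesions, each beginning "Mean absolute difference in the BBL treated arms as compared to the non-treated arms of those with senile purpura". Section 3.2.2 has "Mean absolute difference between the treated and non-treated arms in the change of total square area and number of ecchymoses". Section 3.1 describes the measurement itself: the subjects' "number and square area of ecchymoses will be measured by an evaluator".

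**The concern.** A paired t-test estimates a mean within-subject difference, for which no effect is 0. An odds ratio compares odds of falling in a category, and no effect is 1. It needs a binary or ordinal outcome and a method suited to the design, which here means one for matched arms. The named test does not produce the quantity that is to be reported.

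The sentence is the plan's only rule for the primary effect measure and its confidence interval. An analyst must either depart from it or supply a definition of response that the plan does not contain. Choosing a cut-point after seeing the data could influence the result, and any cut-point would discard the size of the effect. Nothing in the documents suggests that anyone intends to dichotomise.

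The estimate and its precision matter particularly here. Section 8.4 gives no sample size calculation because this is a pilot, and a later trial would be planned from those two figures.

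**Working it through.** **1. Scale of each element**

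| Element | Where | Scale |
|---|---|---|
| Primary endpoints: area and number | Synopsis; section 3.2.2 | Mean difference |
| Measurement | Section 3.1 | Count and area |
| Parameter and null value | SAP; section 8.1 | Mean difference, null 0 |
| Test | SAP; section 8.1 | Mean paired difference |
| Distribution check | SAP; section 8.1 | Numeric data, normality |
| Reported effect | SAP; section 8.1 | Odds ratio, null 1 |

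Only the last row is out of line. The term odds ratio appears nowhere else. The documents contain no responder rule, cut-point, logistic or ordinal model, or matched-pair binary method, for the primary or the secondary endpoints.

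**2. Figure to reproduce**

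There is none. The plan gives no SD, effect size, power or significance level.

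**3. The interval that the plan can support**

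For *n* pairs with mean difference *d* and SD of the paired differences *s*, the two-sided 95% interval is *d* ± t(0.975, n−1) × *s*/√n. In units of *s* the half-width is t(0.975, n−1)/√n.

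The number of pairs is not settled. The synopsis has ten subjects, five of them over 65 with a lesion on each arm, and limits the primary endpoints to those with senile purpura. Section 3.1 speaks of 5 subjects being randomised, without mentioning purpura. Section 4.1 requires ecchymosis on each arm of every participant. I therefore show a range:

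- 5 pairs: 2.776/2.236 = 1.24 SD
- 4 pairs (one of five lost): 3.182/2.000 = 1.59 SD
- 10 pairs: 2.262/3.162 = 0.72 SD

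These figures describe the precision available on the correct scale. They do not measure the odds-ratio error.

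**4. What an odds ratio would look like (illustration only)**

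Suppose each arm were classed as responding or not, by a rule that the plan does not contain. Let *b* pairs respond only on the treated arm and *c* only on the untreated arm. The matched-pair odds ratio is b/c. Its exact limits are p/(1−p), where *p* runs over the Clopper-Pearson limits for b/(b+c).

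- 5 pairs, 5:0. The lower limit of *p* is 0.025^(1/5) = 0.478, and 0.478/0.522 = 0.92. The odds ratio is infinite, with interval 0.92 to infinity.
- 5 pairs, 4:1. Odds ratio 4.0, interval 0.40 to 197.
- 10 pairs, 9:1. Odds ratio 9.0, interval 1.25 to 394.

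With 5 pairs, even the most favourable result possible leaves 1 inside the interval.

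**5. Sign of the difference**

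The alternative is that the parameter exceeds zero, so benefit should come out positive. Take invented counts: treated arm 6 to 2, untreated arm 6 to 5.

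- Change, treated minus untreated: (−4) − (−1) = −3, opposite to the alternative.
- Reduction, treated minus untreated: 4 − 1 = +3, in agreement with it.

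**The case against.** The strongest reply is that this is one stray sentence in a pilot. The endpoints, the parameter, the null value and the test all point to the same quantity, so a competent analyst would report the mean difference anyway. The p-value would not change, and the risk of a post hoc cut-point is hypothetical. All of that is true. It amounts to saying that the SAP should not be followed as written, and the sentence concerns the primary effect measure in both texts.

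The sentence refers to the results of the analysis in general, so it might be meant for side effects, some of which could be coded yes or no. But it stands under the primary-endpoint heading, between the paired t-test and the normality check, and no odds-ratio analysis is defined for any secondary endpoint.

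Two further points stand and are carried into the fix:

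- **Sign.** The documents call the difference absolute and fix no sign, so a signed reduction is a choice that must be stated. An unsigned reading is hard to sustain: the mean of unsigned differences is zero only if both arms change identically in every subject.
- **Sidedness.** The alternative is one-sided as written, so the plan must say that the 95% interval is two-sided.

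**Conclusion.** The concern holds, and the sentence must be corrected. The reporting rule for the primary result is wrong as written, rather than merely short of detail, because the planned analysis cannot yield an odds ratio.

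The consequence is confined to the effect measure and its interval. The size of the error cannot be stated, since no binary outcome exists from which to compute an odds ratio. On the scale that the plan does support, the half-width of the 95% interval runs from 0.72 SD (10 evaluable pairs) to 1.24 SD (5 pairs) and 1.59 SD (4 pairs). This assumes normally distributed paired differences. The SD is not in the documents, so no width in lesions or area can be given.

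**What to change.** In the SAP and in section 8.1, replace the odds-ratio sentence with text such as:

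> For each primary endpoint (number of ecchymoses; total square area of ecchymoses), the mean within-subject difference in reduction from Day 0 to Day 51 will be reported in the units measured, with its two-sided 95% confidence interval from the paired t distribution. The difference is treated-arm reduction minus untreated-arm reduction, so that positive values favour treatment. Individual subject differences will be listed.

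In the second hypothesis item, change size to total square area, so that it matches the synopsis and section 3.2.2. The sponsor should confirm the sign convention, and should state how the two-sided interval relates to the one-sided alternative.

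If an odds ratio is also wanted, add it as a supplementary analysis. The definition of response for each arm and the matched-pair method should both be fixed before the data are seen.

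The cost is one sentence and one term, each changed in two places, plus the short statement on sidedness. The design, data collection, endpoints and test stay as they are.
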